## METHODOLOGY

### Study design

- This is a non-inferiority, blinded, randomized control trial designed to investigate if EOD iron is comparable to daily iron dosing in achieving iron replete status by Ret-Hb measurements in premature infants.

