## Data Analysis

- A sample size determination was conducted using Riskcalc.org (Chow S-C, Shao J, Wang H, Lokhnygina Y. Sample Size Calculations in Clinical Research. Third ed: Chapman and Hall/CRC; 2017.) and confirmed by [name] (BAMC Statistician). Sample size estimates are for type 1 error of 5% ( $\alpha = 0.05$ ), power ( $1-\beta$ ) of 80%, ratio of 1:1 of intervention to control. The effect size is determined by estimating the proportion of infants with Ret-Hgb >29 pg to be similar at 80% between daily versus EOD iron, with a margin of 20%. It was determined that a sample size of 100 patients would be needed for this study (50 for intervention, and 50 for control).
- A statistician who is blinded to the study allocation will analyze the data. All statistical analyses will be performed with IBM SPSS Statistics (Armonk, NY: IBM Corp) and JASP Team (2022). JASP, Version 0.16.1 (Netherlands: JASP Team). Descriptive statistics will be performed for all variables. Categorical data will be reported as percentages, and continuous data will be reported as medians with interquartile range or means with standard deviation. The two groups will be compared according to the intention to treat with the use of Student's t-tests, Mann-Whitney-U tests, chi-square analysis based on the outcome being evaluated. All p-values will be one-sided, with a statistical significance level of <0.05. Covariates to include gestational age, in-born versus out-born infants, ESA use, receipt of pRBC transfusion will be controlled for using a logistic regression model and will be reported with an odds ratio (OR) and 95% confidence intervals (CI). A medical monitor who is not involved in the study will be assigned prior to the initial enrollment of the trial to monitor the data periodically (every 3 months) to ensure the safety of the participants and the scientific integrity of the study. An interim analysis will be performed at halfway to target enrollment.

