## Identified Risks/Ethical Considerations

- The risks associated with iron deficiency include anemia (and associated symptoms to include tachycardia, tachypnea, increased oxygen requirement, increased apnea/bradycardia/desaturation events which can lead to unnecessary evaluations for sepsis and antibiotic administration), long-term neurodevelopmental impairment, increased risk for necrotizing enterocolitis, packed red blood cell (pRBC) transfusion and transfusion-related risks, as well as delayed growth. The overall risk of iron deficiency will be mitigated by monitoring the complete blood count and reticulocyte count for hemoglobin/hematocrit levels and Ret-Hb levels every two weeks. There is no evidence to suggest EOD

iron dosing will result in worse outcomes compared to daily iron dosing. However, outcomes will be monitored every three months to ensure there are no significant adverse outcomes which would warrant study cessation.

- Current practice for frequency of phlebotomy varies by institution but the recommended frequency of lab draws in this study are within normal standards for preterm infants of this gestational age.
- A medical monitor who is not involved in the study will be assigned prior to the initial enrollment of the trial to monitor the data periodically (every 3 months) to ensure the safety of the participants and the scientific integrity of the study.

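### Does the unexplained interim analysis at half enrolment raise the type I error above the planned 5%?

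*Protocol*

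**What the plan says.** The Study design section states "This is a non-inferiority, blinded, randomized control trial". Data Analysis gives the planning basis: "Sample size estimates are for type 1 error of 5" per cent, power "of 80%, ratio of 1:1 of intervention to control", and the proportion of iron-replete infants taken "to be similar at 80% between daily versus EOD iron, with a margin of 20" per cent. From this it concludes that "a sample size of 100 patients would be needed for this study (50 for intervention, and 50 for control").

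Later in the same section, after the software, the descriptive statistics and the list of tests, comes the general rule: "All p-values will be one-sided, with a statistical significance level of <0.05". The section then describes covariate adjustment and a three-monthly review by an independent medical monitor, and closes with "An interim analysis will be performed at halfway to target enrollment".

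Two other places bear on the point. Identified Risks/Ethical Considerations says that "outcomes will be monitored every three months to ensure there are no significant adverse outcomes which would warrant study cessation". Duration of Study says that accrual goes on until the number from the sample size calculation has been reached. The protocol says nothing else about stopping or about early conclusions.

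**The concern.** The planned 50 per arm is reached only if the whole one-sided 5% goes to a single test. The protocol nevertheless schedules an extra look and states one unadjusted level for all p-values. Safety already has its own three-monthly review, so a separate look timed by enrolment, and placed in the analysis section, could be taken as a test of the primary endpoint. If a nominally significant result there could be claimed, every-other-day iron would have two chances to be declared non-inferior by error.

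The situation would not be rare. If both arms truly reach 80%, an interim test at one-sided 0.05 would be significant in more than half of trials. It could also be argued that an interim boundary set in the statistical analysis plan would conflict with the all-p-values sentence, so that only the protocol could put this right.

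**Working it through.** **Inputs.** From Data Analysis: 80% in both arms, margin 20 percentage points, one-sided α = 0.05, power 80%, 50 per arm, one look at half of target enrolment. Assumed here, because the protocol does not say so: the primary comparison is a margin-based z-test on the difference in proportions with unpooled variance.

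**1. The plan's sample size.**

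n per arm = (1.645 + 0.842)² × (2 × 0.8 × 0.2) / 0.2² = 6.185 × 8 = 49.5, so 50.

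With n = 50, SE = √(0.32/50) = 0.08, the standardised distance is 0.2/0.08 = 2.5, and power = Φ(2.5 − 1.645) = 80.4%. A one-sided 0.025 would give (1.960 + 0.842)² × 8 = 62.8, so 63 per arm. The stated 100 infants therefore correspond to one test at one-sided 0.05.

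**2. If success may be claimed at both looks at one-sided 0.05.** With information fraction t at the interim, the two test statistics have correlation √t, and

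overall error = 1 − P(Z₁ < 1.645, Z₂ < 1.645).

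| t | Overall one-sided error |
|---|---|
| 0.5 | 8.0% |
| 0.4 | 8.3% |
| 0.3 | 8.6% |

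At half of target enrolment at most 50 of 100 infants can have a 36-week result, so t is 0.5 or lower and larger fractions do not apply. A simulation of the binomial test at the margin (80% v 60%, 25 then 50 per arm) gives 5.4% at the interim alone, 5.0% at the final alone and 8.4% overall.

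If both arms are truly at 80%, the chance of p < 0.05 at t = 0.5 is Φ(2.5 × √0.5 − 1.645) = Φ(0.123) = 55% (57% in the simulation).

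**3. If no success claim is made at the interim.** Non-inferiority can be concluded only when Z₂ > 1.645 at the end, so

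overall error = P(trial not stopped and Z₂ > 1.645) ≤ P(Z₂ > 1.645) = 5%.

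Stopping for harm or for futility can only lower this. A check of the assumed 80% rate or of data quality leaves it at 5%.

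**4. Which case does the protocol describe?**
- Duration of Study: accrual runs to the target number.
- Identified Risks/Ethical Considerations: adverse outcomes are the only ground given for ending the study.
- Data Analysis: no early conclusion on the primary endpoint is mentioned.

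Together these describe case 3. Case 2 needs a permission that appears nowhere.

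**5. If an early claim were wanted after all.** Lan-DeMets O'Brien-Fleming spending at t = 0.5 uses one-sided 0.0056 at the interim and 0.0482 at the end. It holds 5%, and power with the same 100 infants is 80.1% against 80.4%. A statistical analysis plan could adopt this at a cost of 0.3 points of power and no extra infants.

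**The case for a change.** The strongest argument for a change is that the protocol is not merely silent: it fixes one level for all p-values and plans an interim analysis beside it. Taken literally, that covers an interim test of the primary endpoint. Safety has its own review, so a second look needs some other purpose. An error of 8.0% instead of 5% is a 60% relative increase (8.0/5 = 1.6), in a design that already uses one-sided 5% and a 20-point margin. One sentence would settle the matter.

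Part of this stands. The purpose of the look is not stated, the arithmetic is right, and the purpose has to be fixed before anyone sees comparative interim data. The rest does not carry the conclusion:

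- The all-p-values sentence follows the list of tests and reads as a general convention. A specific interim level in the analysis plan would more naturally refine it than contradict it.
- Safety and efficacy are not the only possible purposes. Futility, a check of the assumed rate, and data quality are ordinary ones. The interim sentence directly follows the one on the medical monitor, whose remit also covers the scientific soundness of the study.
- A p-value computed at the interim does not itself inflate the error. A success claim resting on it would, and the protocol does not allow for one.

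**Conclusion.** No change to the protocol is called for. As written, it describes accrual to 100 infants, cessation only for adverse outcomes, and a final primary test at one-sided 0.05, which keeps the type I error at 5%. The 8.0% (up to 8.6% with fewer 36-week results at the look) rests on two assumptions that the protocol does not make: that non-inferiority may be claimed at the interim, and that the claim would use an unadjusted margin-based test at one-sided 0.05.

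The gap is the purpose and decision rule of the interim look. These are commonly set in the statistical analysis plan, and a trial statistician would settle them there before the look, either by making no primary claim or by using a spending boundary. Neither choice needs more infants. The conclusion would change if another trial document allowed an early non-inferiority claim at the unadjusted level.

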## Data Management

- Collected data will be entered into and managed within REDCap for effective safeguard of information. No physical or hard copies of the data will be made available. The information will be kept confidential by de-identifying the data before it is entered into REDCap. Standard confidentiality measures will be taken. All members of the study team are updated with their CITI/HIPAA training. Results will be presented in table as well as boxplots.

## Identified Risks/Ethical Considerations

- The risks associated with iron deficiency include anemia (and associated symptoms to include tachycardia, tachypnea, increased oxygen requirement, increased apnea/bradycardia/desaturation events which can lead to unnecessary evaluations for sepsis and antibiotic administration), long-term neurodevelopmental impairment, increased risk for necrotizing enterocolitis, packed red blood cell (pRBC) transfusion and transfusion-related risks, as well as delayed growth. The overall risk of iron deficiency will be mitigated by monitoring the complete blood count and reticulocyte count for hemoglobin/hematocrit levels and Ret-Hb levels every two weeks. There is no evidence to suggest EOD

iron dosing will result in worse outcomes compared to daily iron dosing. However, outcomes will be monitored every three months to ensure there are no significant adverse outcomes which would warrant study cessation.

- Current practice for frequency of phlebotomy varies by institution but the recommended frequency of lab draws in this study are within normal standards for preterm infants of this gestational age.
- A medical monitor who is not involved in the study will be assigned prior to the initial enrollment of the trial to monitor the data periodically (every 3 months) to ensure the safety of the participants and the scientific integrity of the study.

### **Benefits of Proposed Research to the Subjects and Others (significance of your study)**

- This will give us insight if EOD iron is equivalent to daily iron supplements. This may also benefit hospital costs as it can help reduce total iron utilization for the duration of the neonate's hospitalization. This study may also help researchers and clinicians gain insight if EOD iron is as efficacious as daily iron in achieving iron replete status in premature infants with the potential of minimizing the side effects of oral iron intake. Participants will not receive compensation for participating in this trial.

## ATTACHMENTS

- **Data collection spreadsheet**
- **Consent Form**
